4.2.2. Computing Environment

All descriptive statistical analyses will be performed using SAS statistical software (Version 9.4), unless otherwise noted. Medical history and adverse events will be coding using MedDRA version 'MedDRA v22.0 - Mar 2019'. Concomitant medications will be coded using World Health Organization (WHO) Drug version 'B3 WHO Drug Global – Mar 2020'.

4.2.3. Methods of Pooling Data

Not applicable to the present study.

4.2.4. Adjustments for Covariates

No formal statistical analysis that adjusts for possible covariate effects is planned.

4.2.5. Multiple Comparisons/Multiplicity

Multiplicity is not of concern for this study since no p-values will be reported.

4.2.6. Subpopulations

No analyses of subpopulations of patients are planned.

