5.3 Expansion Phase (*Phase 2a*)

Patients enrolled into the trial during the Expansion Phase (*Phase 2a*) will be treated at the RP2D level, determined in Phase I to be 1200 µg/kg IM Q6W, as defined in Section [5.2.2](#).

The Phase 2a is designed to evaluate the anti-tumor effects of NT-I7 in combination with atezolizumab in a total of 60 patients. Twenty-four patients in Arm I, i.e., 12 patients for each indication (cSCC and MCC), and 36 patients in Arm II, i.e., 12 patients for each indication (MCC, cSCC and melanoma), will be enrolled. Enrolled patients will be separated into two arms depending on previous use of anti-PD-1/anti-PD-L1 therapy and cancer type.

Arm I (n=24): Anti-PD-1/PD-L1 naïve patients with cSCC (n=12) and MCC (n=12)

Arm II (n=36): Anti-PD-1/PD-L1 relapsed/refractory patients with MCC (n=12), cSCC (n=12) and melanoma (n=12)

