The Phase 2a is designed to evaluate the anti-tumor effects of NT-I7 in combination with atezolizumab in a total of 60 patients. Twenty-four patients in Arm I, i.e., 12 patients for each indication (cSCC and MCC), and 36 patients in Arm II, i.e., 12 patients for each indication (MCC, cSCC and melanoma), will be enrolled. Enrolled patients will be separated into 2 arms depending on previous use of anti-PD-1/PDL-1 therapy and cancer type (see Section 5).

15.3 **Sample Size/Accrual Rate**

During the dose escalation phase (Phase 1b), a 3+3 design will be used for identifying the MTD and/or the RP2D. The following design will be used:

Number of Patients with DLT at a Given Dose Level	Escalation Decision Rule
0 out of 3	Enroll 3 patients at the next dose level.
1 out of 3	Enroll at least 3 more patients at this dose level. 
 • If 0 of these 3 additional patients experience a DLT (totaling 1/6), escalate to the next dose level. • If ≥ 1 of these 3 additional patients experiences DLT (totaling $\geq 2/6$ at the dose level), the dose escalation is stopped, and the next lower dose level will be declared the MTD. In the case this happens at the 120 $\mu\text{g}/\text{kg}$ dose level, a lower dose of 60 $\mu\text{g}/\text{kg}$ will be tested, and the same 3+3 design followed.
≥ 2 out of 3	Dose escalation will be stopped. The next lower dose level will be declared the MTD. Three (3) additional patients will be entered at the next lower dose level if only 3 patients were treated previously at that dose. In the case this happens at the 120 $\mu\text{g}/\text{kg}$ dose level, a lower dose of 60 $\mu\text{g}/\text{kg}$ will be tested, and the same 3+3 design followed.

Abbreviations: DLT=dose-limiting toxicity; MTD=maximum tolerated dose.

Once all patients in a cohort have completed the 3-week DLT window, all AEs will be assessed by the Data and Safety Monitoring Committee.

In the dose expansion phase (Phase 2a), a total of 60 patients will be treated at the RP2D as defined above.

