2. STUDY DESIGN

2.1. Synopsis of Study Design

This is a Phase 1b/2a, open-label, multicenter study to evaluate the safety, tolerability and anti-tumor effect of NT-17 (recombinant human interleukin 7 [rhIL-7]-hybrid Fc [hyFc]) in combination with atezolizumab (MPDL3280A) in patients with anti-PD-1/PD-L1 naïve or relapsed/refractory high-risk skin cancers including cSCC, MCC and melanoma.

This study has been designed to allow for an investigation of MTD or RP2D of NT-17 in combination with atezolizumab. There are two phases to this study:

[figure not shown]
- Phase 1b, a NT-17 dose escalation phase to determine the MTD or RP2D
- Phase 2a, a non-randomized parallel dose expansion phase to confirm the MTD or RP2D in both arms

Arm I: Anti-PD-1/PD-L1 (checkpoint inhibitors [CPI]) naïve patients with cSCC and MCC
Arm II: Anti-PD-1/PD-L1 relapsed/refractory patients with MCC, cSCC and melanoma

Number of Patients

Approximately 84 patients will be enrolled; up to 24 patients will be enrolled in the Phase 1b (3 + 3 dose escalation design will be used), and approximately 60 patients will be enrolled in the Phase 2a (24 patients in Arm I, i.e., 12 patients for each indication, and 36 patients in Arm II, i.e., 12 patients for each indication).

Sponsor:	NeolimmuneTech, Inc.		
Protocol:	NIT-106 (ION-02)		
Document Version No.:	1.0	Document Date:	20Nov2023

Figure 1 Phase 1b\2a Schema

Each patient will participate in the trial ("enrolled") from the time the Informed Consent Form (ICF) is signed through final protocol-specified contact. The active study will end when the last patient completes the 90-day safety follow up visit, approximately 27 months after enrollment. Trial is expected to be completed approximately 36 months after the last patient is enrolled.

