4. STATISTICAL METHODS

4.1. Sample Size Justification

During the dose escalation phase (Phase 1b), a 3+3 design will be used for identifying the MTD and/or the RP2D. The following design will be used:

Number of Patients with Dose-Limiting Toxicity (DLT) at a Given Dose Level	Escalation Decision Rule
0 out of 3	Enroll 3 patients at the next dose level.
1 out of 3	Enroll at least 3 more patients at this dose level. 
- If 0 of these 3 additional patients experience a DLT (totaling 1/6), enroll at the next dose level.- If ≥ 1 of these 3 additional patients experiences DLT (totaling $\geq 2/6$ at the dose level), the dose escalation is stopped, and the next lower dose level will be declared the MTD. In the case this happens at the 120 $\mu\text{g}/\text{kg}$ dose level, a lower dose of 60 $\mu\text{g}/\text{kg}$ will be tested, and the same 3+3 design followed.
≥ 2 out of 3	Dose escalation will be stopped. The next lower dose level will be declared the MTD. Three (3) additional patients will be entered at the next lower dose level if only 3 patients were treated previously at that dose. In the case this happens at the 120 $\mu\text{g}/\text{kg}$ dose level, a lower dose of 60 $\mu\text{g}/\text{kg}$ will be tested, and the same 3+3 design followed.

Based on the available data (Section 2.2 of the protocol), the average historical ORR for the patients in this study would be 45.25% in Arm I and less than 5% in Arm II. With a total of 24 patients treated at the RP2D in Phase 2a of the study in Arm I, the 95% confidence interval for an observed ORR of 17/24 or higher would exclude 45.25%. With a total of 36 patients treated at the RP2D in Phase 2a of the study in Arm II, the 95% confidence interval for an observed ORR of 6/36 or higher would exclude 5%.

Sponsor:	NeolimmuneTech, Inc.		
Protocol:	NIT-106 (ION-02)		
Document Version No.:	1.0	Document Date:	20Nov2023

Approximately 84 patients will be enrolled in this study; up to approximately 24 patients in the Phase 1b and approximately 60 patients in the Phase 2a of the study. The expected accrual is 4 patients per month total at approximately 8 ION sites.

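### Phase 2a plans about 12 patients in each of five arm-by-indication cohorts, but the SAP tabulates no response rate for cSCC, MCC or melanoma within either arm

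*SAP*

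**What the plan says.** SAP 2.1 gives the Phase 2a enrolment as "24 patients in Arm I, i.e., 12 patients for each indication, and 36 patients in Arm II, i.e., 12 patients for each indication". Protocol 5.3 and 15.2.2 plan the same numbers; for Arm II, Protocol 15.2.2 states "12 patients for each indication (MCC, cSCC and melanoma), will be enrolled". The totals are approximate (about 60). Protocol 4.1 also writes the disease eligibility separately for each tumor within each arm.

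The precision statement is per arm. SAP 4.1, repeating Protocol 15.3, says "the average historical ORR for the patients in this study would be 45.25% in Arm I and less than 5% in Arm II", and names 17/24 and 6/36 as results whose 95% interval clears those rates. Protocol 15.5.1 says the Phase 2a analyses will be done separately for each arm. Neither document promises an ORR by indication.

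For the analysis, SAP 4.2.6 says "No analyses of subpopulations of patients are planned". SAP 4.2.1 puts efficacy into two groups: the three lower Phase 1b dose levels, and the 1200 µg/kg level from both phases. SAP 4.8.1 gives numbers and percentages for best overall response, ORR and DCR, with no split by tumor. It also provides listings of tumor assessments and responses. SAP 4.5 provides a by-patient baseline listing and counts diagnosis among the baseline characteristics. SAP 5 records that the study closed early and that responses were few.

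**The concern.** Response rate is the primary objective of Phase 2a, and tumor type within arm is the unit by which its patients are enrolled. An expansion phase of this kind is normally read cohort by cohort, because the next decision is which tumor, if any, to take forward. Under SAP 4.2.1 and 4.2.6 the summary tables cannot support that reading: the 1200 µg/kg column mixes both phases, both arms and all three tumors. Activity in one tumor and none in the others would appear as a single low average, with no table giving the numerator and denominator for the tumor that responded.

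**Working it through.** **Inputs.** Cohort sizes are 12 each, arm sizes 24 and 36, and the Phase 2a total 60 (Protocol 5.3; SAP 2.1). Benchmarks are 45.25% for Arm I and 5% for Arm II, using the upper end of the stated 'less than 5%' (SAP 4.1). Planned enrolment is assumed throughout; the documents do not give the sizes reached.

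**Formula.** Exact (Clopper-Pearson) 95% limits for k responses in n: lower = 2.5% quantile of Beta(k, n-k+1); upper = 97.5% quantile of Beta(k+1, n-k).

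**1. The plan's own cut-offs reproduce.**
- Arm I: 17/24 gives 48.9-87.4%, which excludes 45.25%; 16/24 gives 44.7-84.4%, which does not.
- Arm II: 6/36 gives 6.4-32.8%, which excludes 5%; 5/36 gives 4.7-29.5%, which does not.

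Wilson, Wald, Agresti-Coull and Jeffreys intervals do not give both cut-offs, so the exact interval is the one to use below.

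**2. Four responses, all in one Arm II tumor, none elsewhere.**

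| Denominator | Rate | Exact 95% CI | Excludes 5%? |
|---|---|---|---|
| Cohort, 4/12 | 33.3% | 9.9-65.1% | yes |
| Arm II, 4/36 | 11.1% | 3.1-26.1% | no |
| All Phase 2a, 4/60 | 6.7% | 1.8-16.2% | no |

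The SAP's pool also adds the Phase 1b patients at 1200 µg/kg. With 3 or 6 of them under the 3+3 design, and no response among them, the rate is 4/63 = 6.3% (1.8-15.5%) or 4/66 = 6.1% (1.7-14.8%).

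**3. How often an arm average would miss a single active tumor.** Let one Arm II tumor have true ORR p and the other two 5%. The arm count is Binomial(12, p) + Binomial(24, 0.05). The smallest cohort count whose interval excludes 5% is 3/12 (5.5-57.2%).

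| p | P(arm reaches 6/36) | P(that cohort reaches 3/12) |
|---|---|---|
| 20% | 0.14 | 0.44 |
| 30% | 0.34 | 0.75 |
| 40% | 0.59 | 0.92 |

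This is not a like-for-like comparison of tests. At a true 5%, the chance of reaching the cut-off is 0.0083 for the arm and 0.0196 for one cohort. For at least one of three cohorts it is 1 - (1 - 0.0196)^3 = 0.058. The table shows what averaging hides; it does not propose a decision rule.

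**4. What the pooled figure would mean.** If both arms only matched their benchmarks, the Phase 2a average would be (24 × 0.4525 + 36 × 0.05)/60 = (10.86 + 1.80)/60 = 21.1%, which describes neither arm.

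**5. Precision at n = 12.** 0/12 gives 0-26.5%; 3/12 gives 5.5-57.2%; 6/12 gives 21.1-78.9%. In Arm I a cohort would need 10/12 (51.6-97.9%) to exclude 45.25%, so its cohort rates would be descriptive and little more.

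**The case against.** The strongest defence is that the arm, not the indication, is the protocol's unit of inference. The benchmarks are per arm, Protocol 15.5.1 promises arm-level analyses, and Protocol 15.4 lists no stratification factors. That stands: leaving out rates by indication breaks no commitment.

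Three stronger readings are tempting, and the documents do not support them.

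- **A reader might infer that a response confined to one tumor could not be seen at all.** SAP 4.8.1 lists responses by patient, SAP 4.5 lists baseline data, and SAP 4.2.8 puts all recorded data into listings. Responders could be matched to tumors by hand. What is missing is a tabulated count, denominator and interval.
- **A reader might infer that the cohort quotas serve no purpose.** Equal quotas also hold the tumor mix steady, which helps when an arm is compared with an average historical rate.
- **A reader might infer from Protocol 2.2 that the tumors have different historical rates.** That section presents the rates as similar. The cSCC figure of 47% lies inside the MCC range of 33-56%. Melanoma enters Phase 2a only in Arm II, whose benchmark is below 5%, and no tumor-specific rates are given for relapsed or refractory disease.

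It can also be said that 12 patients are too few and that the study closed early with few responses. The first argues for labelling the table descriptive. SAP 4.2.5 plans no p-values, so there is no multiplicity cost. The second means cohort sizes are unknown, which is a reason to print the actual n.

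**Conclusion.** The point holds as a worthwhile improvement to the analysis plan. No planned table gives a response rate for cSCC, MCC or melanoma within an arm, although those are the groups in which Phase 2a patients are enrolled. Pooling can move a result across the plan's own 5% benchmark, as the 4/12 and 4/36 intervals show.

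The size rests on full planned enrolment and on an Efficacy Population that keeps all 12 patients per cohort. The four-response case and the assumed true rates are illustrations, not findings from the trial.

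A reader might infer that the SAP departs from the protocol on indication; it does not. The loss of the arm split through the two-pool rule in SAP 4.2.1 is a separate and firmer discrepancy with Protocol 15.5.1. It matters here because no breakdown by indication within arm can fit under that rule.

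**What to change.** Amend SAP 4.2.6 together with 4.2.1 and 4.8.1; changing 4.2.6 alone would leave it in conflict with the two-pool rule. Suggested text: 'ORR, DCR and best overall response for Phase 2a will also be shown by arm and by indication within arm, separately from Phase 1b patients, with the actual n and exact 95% confidence intervals; descriptive only, no tests.'

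The data are already collected and diagnosis is already a summarized baseline item, so the cost is a few extra table columns. The drawback is wide intervals, wider still if early closure left cohorts below 12, and the table should say so.

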4.2.7. Withdrawals, Dropouts, Loss to Follow-up

Not applicable to this analysis.

Sponsor:	NeolimmuneTech, Inc.		
Protocol:	NIT-106 (ION-02)		
Document Version No.:	1.0	Document Date:	20Nov2023

4.2.8. Missing, Unused, and Spurious Data

In general, there will be no imputation of missing data points. All data recorded on the CRF will be included in data listings that will accompany the CSR.

4.2.9. Definition of Baseline

The baseline will be the last measurement obtained prior to the drug delivery on Cycle 1 Day 1 (C1/D1). When no measurements are available on C1/D1, data obtained at screening will be regarded as the baseline measurement.

4.2.10. Study Day

Study day is defined as (study date – C1/D1 date + 1) for post-baseline dates, (study date – C1/D1 date) otherwise. C1/D1 is the actual start date for the first dose of any study treatment.

4.2.11. Years and Months

For any calculations, Years will be 365.25 days and Months will be 30.4375 (or 365.25/12).

4.2.12. Imputation of Partial Dates

Partial Diagnosis dates will be imputed to the earliest Day of the month or year.

Stop date imputation will not be applied to ongoing AEs or concomitant medications.

Missing or partial dates for AEs and prior/concomitant medications will be imputed as follows:

- **Start Date**

- If only the day is missing and the month and year are the same as the month and year of the first dose date of any treatment, then the day will be imputed with the day of the first dose date. Otherwise, the day will be imputed with the first day of the event month.
- If both the day and month are missing and the year is the same as the year of the first dose date of any treatment, then they will be imputed with the month and day of the first dose date. Otherwise, they will be imputed with the date of January 1st of event year.
- If the start date is completely missing, the date will be imputed with the first dose date of any treatment.
- If the stop date is complete and the imputed start date is after the stop date, then the imputed start date will be set to the stop date.

- **Stop Date**

Sponsor:	NeolimmuneTech, Inc.		
Protocol:	NIT-106 (ION-02)		
Document Version No.:	1.0	Document Date:	20Nov2023

- If only the day is missing and the month and year are the same as the month and year of the study discontinuation date, then the day will be imputed with the day of the study discontinuation date. Otherwise, the day will be imputed with the last day of the event month.
- If both the day and month are missing and the year is the same as the year of the study discontinuation, then they will be imputed with the month and day of the study discontinuation date. Otherwise, they will be imputed with the date of December 31st.
- If the stop date is completely missing, then it will be imputed with the study discontinuation date.
- If the imputed stop date is greater than the last contact date, then the imputed stop date will be set to last contact date.

4.2.13. Dose-Limiting Toxicity

Dose-limiting toxicity is defined as any AE occurring within the first 21 days (i.e., C1/D1 through Day 21), that is considered to be at least possibly related to the combination study treatment (atezolizumab and NT-17), and that meets at least one of the non-hematologic or hematologic criteria ([Appendix A](#)).

4.3. Interim Analyses

An interim analysis is not planned for this study.

4.4. Patient Disposition

Patient disposition will be tabulated, including the number of patients who: were screened, enrolled, received study treatment, discontinued treatment and the primary reason for discontinuation, withdrew from the study and the primary reasons for withdrawal, and completed 60- and 90-day follow-up visits.

A by-patient listing of study completion information, including the reason for study withdrawal, if applicable, will be presented.

4.5. Demographic and Baseline Characteristics

A summary of demographic characteristics will be provided by dose group, including summaries of age, sex, race, ethnicity, weight, diagnosis of disease, duration of diagnosis, metastatic site, and ECOG performance status. This summary will be based on the Safety Population by phase 1b and 2a and dose level.

Sponsor:	NeolimmuneTech, Inc.		
Protocol:	NIT-106 (ION-02)		
Document Version No.:	1.0	Document Date:	20Nov2023

A by-patient listing of demographic and baseline data will also be provided.

4.6. Medical History

Medical history will be included in a by-patient listing.

4.7. Study Treatment

Dose intensities will be summarized based on the Safety Population, with phases 1b and 2a presented separately by dose level/arm. Patients who have completed each cycle will be summarized.

The dose intensity of NT-17 and atezolizumab is defined as:

Total actual dose received /duration of treatment(months); where treatment duration is last dose date – first dose date + 1

Dose intensity will be summarized overall for each product.

Study treatment data will be included in a by-patient listing.

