1.2 Schema

Description of Study

This is a Phase 1b/2a, open-label, multicenter study to evaluate the safety, tolerability and anti-tumor effect of NT-I7 (recombinant human interleukin 7 [rhIL]-7-hybrid Fc [hyFc]) in combination with atezolizumab (MPDL3280A) in patients with anti-PD-1/PD-L1 naïve or relapsed/refractory high-risk skin cancers including cSCC, MCC and melanoma.

This study has been designed to allow for an investigation of MTD or RP2D of NT-I7 in combination with atezolizumab. There are two phases to this study:

[figure not shown]
- Phase 1b, a NT-I7 dose-escalation phase to determine the MTD or RP2D
- Phase 2a, a non-randomized parallel dose expansion phase to confirm the MTD or RP2D in both arms.

Arm I: Anti-PD-1/PD-L1 (checkpoint inhibitors [CPI]) naïve patients with cSCC and MCC

Arm II: Anti-PD-1/PD-L1 relapsed/refractory patients with MCC, cSCC and melanoma

Number of Patients

A total of approximately 84 patients will be enrolled; up to approximately 24 patients will be enrolled in the Phase 1b (3 + 3 dose escalation design will be used), and approximately 60 patients will be enrolled in the Phase 2a (24 patients in Arm I, i.e., 12 patients for each indication, and 36 patients in Arm II, i.e., 12 patients for each indication).

[figure not shown]

*Each cohort includes checkpoint inhibitor (CPI) naïve and relapsed/refractory patients with high-risk skin cancer; n=3 or 6 based on the 3+3 study design

^aNT-I7 Dose Interruption

NT-I7 administration will be skipped when the ALC is higher than 10,000 cells/µL on Day 1 of every other cycle, starting on Cycle 3. Blood draws conducted prior to dosing on Day 1 will determine if NT-I7 should be interrupted for the current cycle.

^bStarting with DL4 (1200 µg/kg), NT-I7 dosing is changed from Q3W to Q6W. Atezolizumab dosing remains the same (Q3W).

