5.2.1 Treatment Plan

Patients will have a required *pre-treatment biopsy* (see Section 5.4) to assess tumor micro-environment and level of T-cell infiltration. Therapy can be started before results of the biopsy are reported, as it will not be used to determine therapy.

Based on the pharmacodynamic data obtained from the GX-I7-CA-003 study (Q3W dosing) and preliminary data from other ongoing studies with less frequent dosing schedules, NT-I7 can be given less frequently than Q3W (e.g., Q6W) and will still lead to similar changes in the ALC and other peripheral blood T-cell subsets.

Starting with Dose Level 4 (1200 µg/kg) of the dose escalation phase, NT-I7 will be administered in combination with atezolizumab every 6 weeks (Q6W). The NT-I7 dose will be given at the same dose level administered in Cycle 1.

On Day 1 of *every other* cycle (i.e., Cycle 1, Cycle 3, Cycle 5, etc.), patients will be given a dose of NT-I7 by IM injection before receiving standard atezolizumab (1200 mg, intravenously).

On Day 1 of *every* cycle (21-day cycle), patients will be given a dose of Atezolizumab (1200 mg, intravenously). Atezolizumab will be administered every 3 weeks (Q3W).

PK samples will be collected on all patients during the dose escalation phase of the study (refer to PK timepoints tables for specific draw times, Section [12.3.2](#)).

Complete blood count (CBC) with differential including Absolute Lymphocyte Count (ALC) will be checked at each cycle as standard of care. Research blood samples for T-cell phenotypes, CD4+ and CD8+ cell counts will be collected and tested at selected time points (see Sections [12.1.1](#) and [10](#)).

Starting on Cycle 3, Day 1, NT-I7 administration will be skipped when the ALC is higher than 10,000 cells/ μ L. When automated and manual ALC counts are performed, manual ALC counts will be used if the results are conflicting. A blood draw will be performed prior to dosing on Day 1. The results will determine if NT-I7 should be interrupted for the current cycle. Treatment with atezolizumab will continue every 3 weeks.

Treatment with both study agents may continue for *up to 2 years* (see Section [6.4](#)).

Patients will have a required *post-treatment biopsy* (see Section [5.4](#)) to assess changes in the tumor micro-environment and the level of T-cell infiltration.

5.2.2 *Dose Escalation*

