6.1 Study Treatments Administration

Reported AEs and potential risks are described in Section 8. Appropriate dose modifications are described in Section 7. No investigational or commercial agents or therapies other than those described below may be administered with the intent to treat the patient's malignancy.

Treatment will be administered on an outpatient basis.

Table 3 – Study Treatment Details

Regimen Description					
Agent	Premedications; Precautions	Dose	Route	Schedule	Cycle Length
NT-I7	None specific for NT-I7, but the below can be given prior to NT-I7 dosing ¹	Dose in $\mu\text{g}/\text{kg}^2$	IM	Day 1 of every other cycle (Q6W)	21 days
Atezolizumab	antihistamines or antipyretics/ analgesics ¹	1200 mg	IV	Day 1 of each cycle (Q3W)	21 days

Abbreviations: IM=intramuscular; IV=intravenous.

1 Not permitted for the first dose. Optional for subsequent infusions.

2 Refer to Section 5 for assigned dose level.

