3.1.1. Safety Population

The Safety Population will include all patients who receive at least 1 dose of the investigational regimen. The Safety Population will be the primary set for the analysis of safety and non-efficacy data.

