4.2. General Statistical Methods and Data Handling

4.2.1. General Methods

All output will be incorporated into RTF or PDFs, sorted and labeled according to the International Conference on Harmonisation (ICH) recommendations, and formatted to the appropriate page size(s).

Phase 1b/dose escalation will be presented by dose levels 120 µg/kg, 360 µg/kg, 840 µg/kg, 1200 µg/kg and Total. Phase 2a/dose expansion will be summarized under the 1200 µg/kg dose. Efficacy analysis will analyze two groups of pooled data. The first group will pool 120 µg/kg, 360 µg/kg, and 840 µg/kg doses levels of Phase 1b; and the second group will pool the 1200 µg/kg dose level from both phases.

For categorical variables, summary tabulations of the number and percentage within each category (with a category for missing data) of the parameter will be presented.

Continuous variables will be summarized using mean, standard deviation, median, inter-quartile range (IQR) and range; 95% confidence intervals will be presented where appropriate.

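### SAP 4.7 dose intensity omits the interval covered by the last dose, so on-schedule patients read above plan (42 times for one Q6W NT-I7 dose, 21 times for one Q3W dose) and a skipped NT-I7 dose can be hidden

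*SAP*

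**What the plan says.** SAP 4.7 gives the dose intensity of NT-I7 and of atezolizumab as "Total actual dose received /duration of treatment(months); where treatment duration is last dose date" minus first dose date plus 1. It is summarised for each product in the Safety Population, by phase and dose level or arm. That population has a one-dose threshold: "The Safety Population will include all patients who receive at least 1 dose of the investigational regimen". SAP 4.2.1 fixes the statistics: "Continuous variables will be summarized using mean, standard deviation, median, inter-quartile range (IQR) and range". SAP 4.2.11 fixes the month: "Years will be 365.25 days and Months will be 30.4375 (or 365.25/12").

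The dosing interval differs by product and dose level. Protocol 1.2 states that from Dose Level 4 (DL4) "NT-I7 dosing is changed from Q3W to Q6W. Atezolizumab dosing remains the same (Q3W"), and Protocol Table 3 lists the current NT-I7 schedule as "Day 1 of every other cycle (Q6W"). NT-I7 is therefore on a 21-day interval at DL1 to DL3 and a 42-day interval at DL4 and in Phase 2a; atezolizumab is on 21 days throughout. Protocol 5.2.1 also builds in omitted doses: "Starting on Cycle 3, Day 1, NT-I7 administration will be skipped when the ALC is higher than 10,000" cells/µL, while atezolizumab continues.

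SAP 4.7 has no relative (actual over planned) intensity and no rule for a patient with a single dose. It also does not say whether the two dates belong to the product or to any study agent. The only nearby anchor, SAP 4.2.10, is for any agent: "C1/D1 is the actual start date for the first dose of any study treatment".

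**The concern.** A rate per month is meaningful only if the time covered by every dose in the numerator is also in the denominator. Here the last dose is counted but the time it covers is not. The bias is always upward for an on-schedule patient, and it grows as the number of doses falls, so it is tied to how early the patient stopped.

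This trial is exposed to that. First imaging is at about 9 weeks, so an on-schedule patient who stops there would typically have had two Q6W NT-I7 doses, and SAP section 5 records premature closure. A per-month rate is also the natural way to set Q3W dose levels beside Q6W ones, and the distortion differs between the two schedules. Finally, the table ought to show the shortfall from lymphocyte-triggered skips, and the formula can cancel that shortfall against the missing interval.

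**Working it through.** The documents give no numerical dose intensity, so there is no figure to reproduce. What follows evaluates the SAP's own formula.

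**Inputs.** Month = 30.4375 days (SAP 4.2.11). Interval L = 42 days for NT-I7 at DL4 and in Phase 2a; L = 21 days for NT-I7 at DL1 to DL3 and for atezolizumab. Doses: NT-I7 120, 840 and 1200 µg/kg; atezolizumab 1200 mg. Total dose is taken in µg/kg for NT-I7, which SAP 4.7 does not specify; the ratios do not depend on the unit.

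**Planned rates** (dose × 30.4375 / L):
- NT-I7 1200 µg/kg Q6W: 1200 × 30.4375 / 42 = 869.6 µg/kg/month
- NT-I7 840 µg/kg Q3W: 840 × 30.4375 / 21 = 1,217.5 µg/kg/month
- Atezolizumab 1200 mg Q3W: 1200 × 30.4375 / 21 = 1,739.3 mg/month

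**On schedule, per-product dates.** After k doses the duration is (k−1)L + 1 days, so the ratio to plan is kL / ((k−1)L + 1).

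| Doses | Q6W (L = 42) | Q3W (L = 21) |
|---|---|---|
| 1 | 42/1 = 42 | 21/1 = 21 |
| 2 | 84/43 = 1.95 | 42/22 = 1.91 |
| 4 | 168/127 = 1.32 | 84/64 = 1.31 |
| 6 | 252/211 = 1.19 | 126/106 = 1.19 |
| 18 | 756/715 = 1.06 | 378/358 = 1.06 |
| 35 | not applicable within 2 years | 735/715 = 1.03 |

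For Q6W NT-I7 at 1200 µg/kg, one, two and four doses give 36,525, about 1,699 and about 1,150 µg/kg/month, against 869.6 planned.

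**On schedule, any-agent dates, Q6W NT-I7.**
- Cycle 1 only: 42/1 = 42
- Atezolizumab at Cycles 1 and 2: 42/22 = 1.91
- Treatment ending at Cycle 4: 84/64 = 1.31

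The ratio exceeds 1 under both readings, and the 42 and 21 figures for a patient treated on Cycle 1 Day 1 alone are the same under both.

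**Comparison across dose levels.** Planned DL3 is 1,217.5/869.6 = 1.4 times planned DL4. For one-dose patients the formula reverses the order: 840 × 30.4375 = 25,567.5 at DL3 against 36,525 at DL4. One DL1 dose gives 120 × 30.4375 = 3,652.5, which is 4.2 times the planned DL4 rate.

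**Interior skip.** NT-I7 at Cycles 1 and 5, Cycle 3 skipped, per-product dates: 2 × 1200 × 30.4375 / 85 = 859.4, or 84/85 = 98.8% of plan, with two of three doses given. With the final interval added: 2 × 1200 × 30.4375 / 126 = 579.8, or 84/126 = 66.7%.

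**Trailing skip.** NT-I7 at Cycles 1 and 3, Cycle 5 skipped, per-product dates: 84/43 = 1.95 times plan, again with two of three doses given.

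**The case against.** The best case against is about weight. The table is descriptive, escalation rests on dose-limiting toxicity counts, and the SAP also provides cycle counts and by-patient listings. The SAP reports an absolute rate, so the reader has to supply the planned rate to see the excess. The 42-fold figure needs a single treatment day, the documents do not say how many such patients there are, and the ratio is close to 1 for long treatment. All of this stands and limits the consequence, but none of it corrects the formula. A completed cycle may have contained atezolizumab alone, and a listing does not repair a summary. The median and interquartile range resist the extremes, but they still shift because every on-schedule patient is biased upward.

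The SAP's wording that intensity is summarised for each product favours per-product dates, so the ambiguity is moderate. Under the any-agent reading a skip can be partly visible: two of three NT-I7 doses with atezolizumab ending at Cycle 6 gives 84/106 = 79%. If atezolizumab ends at Cycle 5, the same shortfall again reads 84/85 = 98.8%.

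The sharpest objection is to the remedy. With per-product dates plus one interval, a trailing skip disappears: NT-I7 at Cycle 1, Cycle 3 skipped, atezolizumab to Cycle 4 gives 42/42 = 100%, where the present formula with any-agent dates would give 42/64 = 66%. That is correct, and it is why the dose count below is a required part of the fix.

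The table shells mentioned in SAP 1.2.3 are not in the text available, so dose counts may already be tabulated there. That would not change the stated formula.

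**Conclusion.** The point holds. As written, the formula overstates dose intensity for every on-schedule patient under either reading of the dates: 42 times plan after one Q6W dose, 21 times after one Q3W dose, just under twice after two doses, about 1.3 times after four, and 1.03 to 1.06 times near two years. It can also present an interior NT-I7 skip as 98.8% of plan when 66.7% is right.

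The ratios rest only on the SAP's formula and the protocol's 21- and 42-day intervals, with doses given exactly on schedule. The absolute rates further assume that NT-I7 dose is totalled in µg/kg. The effect on the reported mean or median cannot be computed, because the distribution of doses received is not given. The consequence is confined to the exposure summary, but that summary feeds the study report. It should be corrected before the tables are produced.

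**What to change.** In SAP 4.7:

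1. State that first and last dose dates are those of the product being summarised.
2. Define duration as last dose date minus first dose date plus the planned interval for the schedule received (21 or 42 days). For k on-schedule doses the ratio to plan becomes kL/(kL) = 1.00 for any k, including one.
3. State the dose unit, and report relative dose intensity (actual over planned, as a percentage).
4. Tabulate, by product and by dose level or arm, doses given and scheduled doses skipped. The rate exposes an interior skip; only the count exposes a trailing one (one of two doses given in the Cycle 1 to 4 example).

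The cost is a few lines of SAP text and a program change using dosing data already collected. The planned interval must be carried by product and dose level, and the exposure figures will look less favourable. No dose, schedule or clinical rule is affected.
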